Appendix B: Biological samples for further ancillary studies

Only German study sites will participate in the biological sampling project.

In the case of patient's consent, the following biological samples will be obtained:

a) Bone marrow cells

- before start of treatment

- during treatment/ at EOT only in those patients in whom bone marrow aspiration is performed to confirm CR or to document delayed response (see Appendix A).

b) Cheek swab

- once before start of treatment

[figure not shown]
c) Peripheral blood and serum

- at different time points as indicated below and in case of progression at any time of the study.

Questions and notifications regarding biological sampling should be sent via e-mail to:

[contact]

Timeline

Time points

Four eligible time points are described for bio-sampling:

1. Prior to treatment
2. C10D1 (during treatment)
3. EOT (month 18)
4. When in progress

Sample	Usage
30 mL of peripheral blood in CELL-FREE DNA blood collection tubes (BCT®) (Streck)	Storage of plasma for cell free DNA (cfDNA), storage of DNA (cell pellet) for MRD measurement
15 mL of bone marrow	
 - Storage of freshly isolated cells - Storage of DNA and RNA from sorted bone marrow B cells
10 mL of serum	Storage of serum proteins
10 mL EDTA	Storage of DNA (cell pellet) for MRD
Cheek swab	Storage of DNA of non-hematopoietic cells (FTA cards)

The biological samples should be sent as follows:

Sample	Delivery
30 ml of peripheral blood	Peripheral Blood should be collected on site in CELL-FREE DNA blood collection tubes (BCT®) (Streck), which will be provided by the Sponsor. Tubes will be sent to the University of Ulm at ambient temperature with overnight carrier for next day delivery
15 ml of bone marrow aspirate	EDTA tube at ambient temperature should be sent to the University of Ulm with overnight carrier for next day delivery
1 x 10 ml of serum	Serum tubes at ambient temperature with overnight carrier for next day delivery
1 x 10 ml EDTA	EDTA tubes at ambient temperature with overnight carrier for next day delivery
Cheek swab	DNA of non-hematological cells will be collected by cheek swabs and the Whatman® FTA® card technology (Sigma-Aldrich). The kit will be provided by the Sponsor. Genomic DNA stored on FTA Cards at room temperature is stable for years. FTA cards will be sent to the University of Ulm with overnight carrier for next day delivery

All the collected biological samples are common property and are open for scientific projects performed by the participants of this trial. Transport costs will be covered by the sponsor of the trial.

Appendix C: Contraceptive Guidance and Pregnancy Testing

Woman of Childbearing Potential (WOCBP)

A woman is considered fertile following menarche and until becoming post-menopausal unless permanently sterile (see below)

Women in the following categories are not considered WOCBP:

- Premenarchal
- Premenopausal female with 1 of the following:
 - Documented hysterectomy
 - Documented bilateral salpingectomy
 - Documented bilateral oophorectomy

Note: Documentation can come from the site personnel's review of the participant's medical records, medical examination, or medical history interview.

- Postmenopausal female
 - A postmenopausal state is defined as no menses for 12 months without an alternative medical cause.
 - A high follicle stimulating hormone (FSH) level in the postmenopausal range may be used to confirm a postmenopausal state in women not using hormonal contraception or hormonal replacement therapy (HRT). However, in the absence of 12 months of amenorrhea, confirmation with two FSH measurements in the postmenopausal range is required.
 - Females on HRT and whose menopausal status is in doubt will be required to use one of the non-hormonal highly effective contraception methods if they wish to continue their HRT during the study. Otherwise, they must discontinue HRT to allow confirmation of postmenopausal status before study enrollment.

1. Contraception Requirements

Male Participants:

Male participants with female partners of childbearing potential are eligible to participate if they agree to one of the following during the protocol defined time frame:

- Be abstinent from penile-vaginal intercourse as their usual and preferred lifestyle (abstinent on a long term and persistent basis) and agree to remain abstinent
- Use a male condom plus partner use of a contraceptive method with a failure rate of <1% per year as described in Table 9 when having penile-vaginal intercourse with a woman of childbearing potential who is not currently pregnant.

- Note: Men with a pregnant or breastfeeding partner must agree to remain abstinent from penile-vaginal intercourse or use a male condom during each episode of penile penetration.

Female Participants:

Female participants of childbearing potential are eligible to participate if they agree to use a highly effective method of contraception consistently and correctly as described in Table 4 during the protocol-defined time frame in.

Table 4 Highly Effective Contraception Methods


Highly Effective Contraceptive Methods That Are User Dependent ^a Failure rate of <1% per year when used consistently and correctly.

 ● Combined (estrogen- and progestogen- containing) hormonal contraception associated with inhibition of ovulation^b 
 ○ Oral ○ Intravaginal ○ Transdermal

 ● Progestogen-only hormonal contraception associated with inhibition of ovulation^b 
 ○ Oral ○ Injectable

Highly Effective Methods That Have Low User Dependency Failure rate of <1% per year when used consistently and correctly.

 ● Progestogen- only contraceptive implant ● Intrauterine hormone-releasing system (IUS) ● Intrauterine device (IUD) ● Bilateral tubal occlusion

 ● Vasectomized partner A vasectomized partner is a highly effective contraception method provided that the partner is the sole male sexual partner of the WOCBP and the absence of sperm has been confirmed. If not, an additional highly effective method of contraception should be used.

 ● Sexual abstinence Sexual abstinence is considered a highly effective method only if defined as refraining from heterosexual intercourse during the entire period of risk associated with the study treatment. The reliability of sexual abstinence needs to be evaluated in relation to the duration of the study and the preferred and usual lifestyle of the participant.)

Notes: Use should be consistent with local regulations regarding the use of contraceptive methods for participants of clinical studies.

- a) Typical use failure rates are lower than perfect-use failure rates (i.e. when used consistently and correctly).
- b) If hormonal contraception efficacy is potentially decreased due to interaction with study treatment, condoms must be used in addition to the hormonal contraception during the treatment period and for at least 110 days after the last dose of study treatment.

Please note: If a patient experiences nausea or diarrhea, oral contraception is not considered a reliable method.

Combined contraceptive methods (additional use of condoms for female participants and their partners) are recommended.

2. Pregnancy Testing

WOCBP should only be included after a negative highly sensitive urine or serum pregnancy test.

Following initiation of treatment, pregnancy testing will be performed whenever an expected menstrual cycle is missed or when pregnancy is otherwise suspected; at the time points specified in the Schedule of Activities, and as required locally.

Appendix D: Selection of Lesions and Response Criteria for Nodal Marginal Zone Lymphoma and Extragastric MALT Lymphoma

Response should be determined on the basis of radiographic and clinical evidence of disease adapting the modified 2007 Cheson criteria below⁵.

Selection of Target Lesions

Up to six of the largest dominant nodes or tumor masses selected according to all of the following:

- Clearly measurable in at least two perpendicular dimensions at baseline
All nodal lesions must measure:
 - 1.5 cm in greatest transverse diameter (GTD) regardless of short axis measurement, or
 - If the GTD measures between 1.1-1.5 cm, the short axis must measure > 1.0 cm.
- All extranodal lesions must measure \geq 1.5 cm in the GTD.
- If possible, the lesions should be from disparate regions of the body
- Should include mediastinal and retroperitoneal areas of disease whenever these sites are involved
- Extranodal lesions within the liver or spleen must be at least 1.5 cm in two perpendicular dimensions.

Selection of Nontarget Lesions

Nontarget lesions will be qualitatively assessed at each subsequent time point. All of the sites of disease present at baseline and not classified as target lesions will be classified as nontarget lesions, including any measurable lesions that were not chosen as target lesions. Examples of nontarget lesions include:

- All bone lesions, irrespective of the modality used to assess them
- Lymphangitis of the skin or lung
- Cystic lesions
- Splenomegaly and hepatomegaly
- Measurable lesions beyond the maximum number of six
- Groups of lesions that are small and numerous
- Pleural/pericardial effusions and/or ascites with cytological evidence of malignancy

Reporting Conventions

Lesion not assessable

This category is reserved for target and non-target lesions that are deemed “not assessable” because:

- One or more target/nontarget cannot be assessed (e.g., inadequate scan coverage, contrast, artifacts, or other factors).
- One or more target/non-target lesions were excised or irradiated and have not reappeared or increased.

Examples of lesions not assessable are a lung lesion in the hilum obstructing the bronchus and causing atelectasis of the lobe or a hypodense liver lesion that becomes surrounded by fatty infiltration. In both examples, the boundaries of the lesion can be difficult to distinguish. Every effort should be made to assign measurements to lesions that develop less distinct margins because they become much smaller.

Effects of Lesions not Assessable on Response Assessment

If a target lesion is classified as not assessable after baseline, the sum of the product of the diameters (SPD)/area (whichever applies) of the target lesions cannot accurately be determined for that time point. In this case the clinical judgment of the investigator together with the measurements of all other assessable lesions is necessary to record the timepoint response.

PD can be determined without evaluation of all sites of disease on the basis of the GTD, area or SPD for target lesions, evaluation of unequivocal progression in nontarget lesions, or observation of a new lesion within the available radiographic or clinical assessments.

Response Criteria for Nodal Marginal Zone lymphoma and extragastric MALT lymphoma and for measurable disease (≥ 1.5 cm) shown by radiographic evidence. For the assessment of extranodal gastric MALT lymphoma and splenic MZL, see Appendices E and F **in addition** to the information below.

Complete Response (CR)

1. Complete disappearance of all detectable clinical evidence of disease and disease-related symptoms if present prior to therapy.
2. Variably FDG-avid lymphomas/FDG avidity unknown: In patients without a pretreatment PET scan, or if a pretreatment PET scan was negative: all lymph nodes and nodal masses must have regressed on CT to normal size (< 1.5 cm in their greatest transverse diameter for nodes 1.5 cm prior to therapy). Previously involved nodes that were 1.1 - 1.5 cm in their long axis and >1.0 cm in their short axis prior to treatment must have decreased to < 1.0 cm in their short axis after treatment.
3. The spleen and/or liver, if considered enlarged prior to therapy on the basis of a physical examination or CT scan, should not be palpable on physical examination and should be considered normal size by imaging studies, and nodules related to lymphoma should disappear. However, determination of splenic involvement is not always reliable as a spleen considered normal in size may still contain lymphoma, whereas an enlarged spleen may reflect variations in anatomy, blood volume, the use of hematopoietic growth factors, or other causes rather than lymphoma.
4. If the bone marrow was involved by lymphoma prior to treatment, the infiltrate must have cleared on repeat bone marrow biopsy. The biopsy sample on which this determination is made must be adequate (with a goal of > 20 mm unilateral core). If the sample is indeterminate by morphology, it should be negative by immuno-histochemistry. A sample that is negative by immuno-histochemistry but demonstrating a small population of clonal lymphocytes by flow cytometry will be considered a CR until data become available demonstrating a clear difference in patient outcome.

Partial Response (PR)

1. $>50\%$ decrease in sum of the product of the diameters (SPD) of up to 6 of the largest dominant nodes or nodal masses. These nodes or masses should be selected according to all of the following: (a) they should be clearly measurable in at least 2 perpendicular dimensions; (b) they should be from disparate regions of the body; (c) they should include mediastinal and retroperitoneal areas of disease whenever these sites are involved.
2. No increase in the size of other nodes, liver or spleen
3. Splenic and hepatic nodules must regress by $\geq 50\%$ in their SPD or, for single nodules, in the greatest transverse diameter.
4. With the exception of splenic and hepatic nodules, involvement of other organs is usually evaluable and not measurable disease.

5. Bone marrow assessment is irrelevant for determination of a PR if the sample was positive prior to treatment. However, if positive, the cell type should be specified, e.g. large-cell lymphoma or small neoplastic B cells. Patients who achieve a complete remission by the above criteria, but who have persistent morphologic bone marrow involvement will be considered partial responders. In cases where the bone marrow was involved prior to therapy that resulted in a clinical CR, but with no bone marrow assessment following treatment, patients should be considered as partial responders.
6. No new sites of disease
7. Variably FDG-avid lymphomas/FDG-avidity unknown; for patients without a pretreatment PET scan, or if a pretreatment PET scan was negative, standard CT criteria should be used.

Stable Disease (SD)

1. Failing to attain the criteria needed for a CR or PR, but not fulfilling those for progressive disease (see below).
2. Variably FDG-avid lymphomas/FDG-avidity unknown
For patients without a pretreatment PET scan or if the pretreatment PET was negative, there must be no change in the size of the previous lesions on the post treatment CT scan.

Progressive Disease (PD)

Lymph nodes should be considered abnormal if the long axis is >1.5 cm regardless of the short axis. If a lymph node has a long axis of 1.1-1.5 cm it should only be considered abnormal if its short axis is >1.0. Lymph nodes < 1.0 cm x <1.0 cm will not be considered as abnormal for relapse or progressive disease.

Appearances of any new lesion > 1.5 cm in any axis during or at the end of therapy, even if others are decreasing in size. Increased FDG uptake in a previously

1. unaffected site should only be considered relapsed or progressive disease after confirmation with other modalities. In patients with no prior history of pulmonary lymphoma, new lung nodules identified by CT are mostly benign. Thus, a therapeutic decision should not be made solely on the basis of the PET without histological confirmation.
2. >50% increase from nadir in the SPD of any previously involved nodes, or in a single involved node, or the size of other lesions (e.g., splenic or hepatic nodules). To be considered progressive disease, a lymph node with a diameter of the short axis of < 1.0 cm must increase by $\geq 50\%$ and to a size of 1.5 x 1.5 cm or > 1.5 cm in the long axis.
3. 50% increase in the longest diameter of any single previously identified node >1 cm in its short axis.
4. Lesions should be PET-positive if a typical FDG-avid lymphoma or one that was PET-positive prior to therapy unless the lesion is too small to be detected with current PET systems (<1.5 cm in its long axis by CT).

Please note, that PET is not part of the regular tumor assessment in this trial and that PET should only be done if medically indicated; so in regular cases judgement about response has to be done without PET information.

Matrix for Timepoint Response Evaluation

Target Lesions	Non-Target Lesions	New Lesions	Timepoint Response
CR	CR	No	CR
CR	SD	No	PR
PR	CR	No	PR
PR	SD	No	PR
SD	CR	No	SD
SD	SD	No	SD
PD	Any	Yes/No	PD
Any	PD	Yes/No	PD
Any	Any	Yes	PD

Appendix E: Response Criteria for Extranodal Gastric Marginal Zone lymphoma (MALT)

The histological grading system of the GELA for posttreatment evaluation of gastric MALT lymphoma should be used⁷. If there is a measurable extragastric extranodal or nodal disease, it should be documented additionally on the basis of radiographic and clinical evidence of disease using the modified 2007 Cheson criteria (see Appendix D).

GELA histological grading system for post-treatment evaluation of gastric MALT lymphoma

Score	Lymphoid infiltrate	LEL	Stromal changes
CR	Absent or scattered plasma cells and small lymphoid cells in the LP	Absent	Normal or empty LP and/or fibrosis
pMRD	Aggregates of lymphoid cells or lymphoid nodules in the LP/MM and/or SM	Absent	Empty LP and/or fibrosis
rRD	Dense, diffuse, or nodular extending around glands in the LP	Focal LEL or absent	Focal empty LP and/or fibrosis
NC	Dense, diffuse, or nodular	Present, "may be absent"	No changes

CR = complete remission, pMRD = probable minimal residual disease, rRD= responding residual disease, NC = no change, MM, muscularis mucosa; LP, lamina propria; SM, submucosa; LEL, lymphoepithelial lesions.

According to this histological scoring system, criteria for treatment response in GMZL can be defined as follow:

1. Complete remission (CR) is defined as normalization of endoscopic findings and negative histology (CR or pMRD) in two subsequent follow-up investigations.
2. Partial remission (PR) is defined as normalization or reduction of macroscopic findings, histological signs of lymphoma regression (rRD) and no signs of progressive disease.
3. Stable disease (SD) is characterized by unmodified gastroscopic findings and/or unmodified histology (NC).
4. Progressive disease (PD) is defined by worsening of macroscopic findings or dissemination of gastric MALT lymphoma or transformation into diffuse large B-cell lymphoma.
5. Relapse is defined as the re-occurrence of histologically- confirmed lymphoma after a CR was previously documented.

Appendix F: Response Criteria Splenic Marginal Zone lymphoma

The following criteria should be used for response evaluation^{6, 15}. Splenomegaly as well as nodal or extranodal disease should be documented using the modified 2007 Cheson criteria⁵ (see Appendix D).

Response Criteria for Splenic MZL Response Category	Definition
Complete response (CR)	
 Resolution of organomegaly, normalization of the blood counts (Hb >12 g /dl; platelets > 100 x 10⁹/l; neutrophils >1.5 x 10⁹/l and no evidence of circulating clonal B cells). No evidence or minor BM infiltration detected by immunohistochemistry.
Partial response (PR)	
 50% or greater improvement in the disease manifestations. This should include resolution or decrease in spleen size, improvement on cytopenias and resolution or decrease in lymphadenopathy if present. BM should show a decrease in the level of lymphoid infiltration and improvement of the hemopoietic reserve.
No response (Stable Disease (SD))*	
 No response: Less than 10% improvement on the disease manifestations
Progressive Disease (PD)*	
 Progressive disease: Deterioration of the above, i.e. > 50% of measurable signs of the disease from nadir.

Splenectomy: Response will be considered when there is at least 50% improvement on the blood counts, non-progressive lymphocytosis and no change or improvement in the degree of BM infiltration.
 
*: Based on (Dreyling, 2013), this category will be split into two separate response categories
	

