5.1 Primary Objective

The objective of the trial is to test the efficacy of treatment with Pembrolizumab and Rituximab in patients with MZL in need of treatment, who have failed or are not eligible for local therapy or relapsed. For efficacy the rate of complete remissions (according to the GELA criteria for gastric MALT or to the Cheson 2007 criteria for nodal and splenic MZL) after end of treatment (18 cycles) will be primarily analyzed.

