9.1.3 Bone marrow examinations

Bone marrow examinations should include a biopsy for morphology and an aspirate for local hematology (optional, if part of standard of care at site). Bone marrow examinations are required at screening for staging purposes in all patients (CR definition requires clearing of a previously infiltrated bone marrow) and must not be older than 12 weeks before start of treatment. If there was bone marrow infiltration at screening, then a subsequent bone marrow biopsy at the completion of cycle 9 is required for clinical response evaluation for all patients who may have achieved a CR. In patients with a PR and continued bone marrow involvement, a subsequent bone marrow examination may be required to confirm a CR at a later time point. An additional bone marrow aspirate may be done if that is standard of care at the site.

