8.2.5 Sensitivity Analyses

Sensitivity analyses are planned for the stability investigation of the result of the confirmatory analysis of the primary endpoint. Patients who withdraw will be excluded from the confirmatory data analysis but will be analysed in a separate exploratory sensitivity analysis. Two distinct scenarios will be regarded to investigate the influence of withdrawals. In a first scenario is the primary endpoint in all withdrawals set to CR='no'. In the second scenario is the primary endpoint in all withdrawals set to CR='yes'.

Another sensitivity analysis is planned for patients with discrepancy between using the modified 2007 Cheson criteria and the data base entries regarding the evaluation of the primary endpoint. If there are such patients, two further scenarios for the primary endpoint will be investigated: In the first scenario the modified 2007 Cheson criteria will be applied, in the second scenario the data base entries as entered by the sites will be used.

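### The plan gives two different bone-marrow requirements for CR in splenic MZL and does not say which one defines the confirmatory endpoint

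*Protocol*

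**What the plan says.** The primary endpoint is the CR rate after 18 cycles, tested against 56% (Protocol 5.2 and 12.3; SAP 8.2.1). Five places bear on what CR means in splenic MZL.

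- **Protocol 5.1** says CR is judged according "to the Cheson 2007 criteria for nodal and splenic MZL". The synopsis and SAP 2.1 also assign splenic MZL to Cheson 2007. None of the three mentions marrow or Appendix F.
- **Protocol 9.1.3**, where screening marrow is mandatory for every patient, gives as the reason that the "CR definition requires clearing of a previously infiltrated bone marrow". It makes no exception for splenic disease.
- **Protocol Appendix D**, the modified Cheson 2007 criteria, states under CR: "If the bone marrow was involved by lymphoma prior to treatment, the infiltrate must have cleared on repeat bone marrow biopsy". Under PR it adds that patients otherwise in complete remission "who have persistent morphologic bone marrow involvement will be considered partial responders".
- **Protocol Appendix F**, the splenic table, opens with "The following criteria should be used for response evaluation". Its CR row allows "No evidence or minor BM infiltration detected by immunohistochemistry". No threshold for minor is given.
- **SAP 7.5** sets CR to yes for a splenic patient when the recorded splenic category at end of treatment is CR. **SAP 8.2.5** plans two scenarios for patients in whom Cheson and the database disagree: "In the first scenario the modified 2007 Cheson criteria will be applied, in the second scenario the data base entries as entered by the sites".

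**The concern.** Take a splenic patient at end of treatment with resolved organomegaly, normal blood counts and no circulating clonal B cells, whose marrow was infiltrated at baseline and still shows a minor infiltrate. Appendix F permits CR. Protocol 9.1.3 does not. If the infiltrate is visible morphologically, Appendix D makes the patient a PR. The same findings can therefore score as success or failure on the trial's only confirmatory endpoint.

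The SAP does not settle this. Its confirmatory variable is whatever category the site recorded, so it inherits whichever page the site followed, and different sites may have followed different pages. If sites used Appendix F, the confirmatory CR rate departs from the criterion in the primary objective, and the Cheson reading appears only as a sensitivity scenario.

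The marrow item is not a rare side issue. Protocol 7.1 requires infiltration of marrow and/or blood for splenic entry, so it can apply to many splenic patients. Splenic MZL also makes up more of the actual sample than planned: 7 of 22 (31.8%) in SAP 2.1, against about 20% in Protocol 12.1.

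**Working it through.** **1. The marrow rules side by side**

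| Source | Applies to | Residual marrow disease compatible with CR? |
|---|---|---|
| Protocol 5.1, synopsis, SAP 2.1 | Splenic MZL, by reference to Cheson 2007 | Not stated; depends on the criteria cited |
| Protocol 9.1.3 | All patients | No; must have cleared |
| Appendix D, CR item 4 | Headed for nodal and extragastric MALT; is the protocol's Cheson 2007 | No; and must be immunohistochemistry-negative if morphology is indeterminate |
| Appendix D, PR item 5 | As above | No; persistent morphologic involvement is PR |
| Appendix F, CR row | Splenic MZL | Yes, if minor by immunohistochemistry |

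**2. Is there a precedence rule?** Protocol 9.1.2 refers to Appendices D to F together. Appendix D says that for gastric and splenic disease Appendices E and F are to be consulted in addition to it. Appendix F refers back to Appendix D for splenomegaly and for nodal or extranodal disease. None of these says which rule governs marrow when the two differ.

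**3. How sharp is the conflict?**
- *Morphologically visible minor infiltrate:* CR is possible under Appendix F; PR under Appendix D; not CR under 9.1.3. This is a direct contradiction.
- *Infiltrate seen only by immunohistochemistry, morphology clearly negative:* CR is possible under Appendix F. Appendix D does not explicitly exclude CR, because it demands immunohistochemical negativity only when morphology is indeterminate and its PR rule concerns morphologic involvement. Protocol 9.1.3 still asks for clearing.

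**4. What one patient is worth.** The plan gives no figure on this point to reproduce. The inputs are 22 enrolled, 7 of them splenic (SAP 2.1), and a one-sided exact binomial test against 56% at 2.5% (SAP 8.2.1).

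- Change in CR rate per reclassified patient: 1/22 = 4.5 points.
- Arithmetic ceiling if all seven were affected: 7/22 = 31.8 points. This is a bound, not an expectation.
- Cut-off: the smallest r with P(X ≥ r | n = 22, p = 0.56) ≤ 0.025.
  - P(X ≥ 17) = 0.0334: not significant.
  - P(X ≥ 18) = 0.0107: significant.
  - So r = 18, an observed rate of 18/22 = 81.8%.

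At exactly 18 CRs, moving one splenic patient from CR to PR leaves 17 and reverses the test. In general, at 18 + j CRs it takes j + 1 such patients.

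**5. If withdrawals reduce n.** SAP section 4 excludes withdrawals. With 21 analysed the cut-off is 17 (p = 0.0158); with 20 it is 16 (p = 0.0233). The cut-off moves, but a single patient can still decide the result at the boundary.

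**The case against.** **Appendix F is the specific rule and therefore governs.** This is the strongest counter-argument. Appendix D is headed for other subtypes. Appendix F says its own criteria should be used, and its instruction to use Cheson does not list marrow. SAP 7.5 describes assessment by subtype-specific criteria. On that reading, 5.1 and 9.1.3 are merely loose summaries. This is plausible, but the protocol says in addition, not instead; 9.1.3 covers all patients without exception; and the objective names Cheson for splenic MZL. The reading has to be inferred, and a confirmatory endpoint should not depend on inference.

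**SAP 8.2.5 already shows both results.** It does make any difference visible. It does not say which is confirmatory; SAP 7.5 does so by default, through the site entry.

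**A reader might infer that the conflict inflates the false-success rate above 2.5%.** The documents do not support a figure. If every subtype had a true CR rate of 56%, and 20%, 40% or 60% of splenic non-CRs were recorded as CR, the chance of at least 18 of 22 would rise from 1.1% to 2.0%, 3.5% or 5.8%. Those fractions appear nowhere in the documents. They also count patients with stable or progressive disease as able to switch, although Appendix F still demands resolved organomegaly, normal counts and no circulating clonal B cells. With the rates in Protocol 12.1 (55.8% MALT, about 60% splenic, about 20% nodal) and the actual 8/7/7 mix, the same calculation gives 0.02% with no switching and 0.05%, 0.09% and 0.15% with it. No Type I error claim should be made.

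**A reader might also infer a bias against the 56% benchmark, or that Appendix D should win.** Neither follows. The documents do not say which marrow rule lies behind the splenic benchmark of about 60%. Pooling subtype-specific CR definitions is also deliberate: Appendix E counts probable minimal residual disease as CR in gastric disease. Appendix F is laxer on marrow only; it adds blood-count conditions that Appendix D lacks.

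**Conclusion.** The contradiction is real and bears on the only confirmatory test. Appendix F allows CR with an undefined minor marrow infiltrate. Protocol 9.1.3 does not, nor does Appendix D where the residual infiltrate is morphologically evident, and nothing sets precedence. For infiltration seen only by immunohistochemistry with clearly negative morphology, the conflict is with 9.1.3 rather than with the explicit wording of Appendix D.

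How many patients are affected cannot be known from the documents: anything from 0 to 7. Each is worth 4.5 points of CR rate if all 22 are analysed, and one is enough to reverse the primary result if the count stands at 18. The result may equally be unaffected. The conclusion rests on the texts and the enrolment figures, not on any assumed misclassification rate. This should be settled before the analysis; it does not show that the trial's conclusion will be wrong.

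**What to change.** Before the analysis:

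1. Reconcile Protocol 5.1, 9.1.3, Appendix D and Appendix F on the marrow requirement for splenic CR. Which rule is right is for the sponsor to decide.
2. State in SAP 7.5 the single marrow rule that defines confirmatory CR for splenic MZL. If the Appendix F wording is kept, define minor, and say how infiltration seen only by immunohistochemistry is treated.
3. Apply that rule uniformly to the existing marrow reports of the splenic patients, at most seven, rather than relying on the recorded category alone.
4. Report the other marrow rule as the sensitivity result in SAP 8.2.5, with the number of patients whose classification differs.

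The cost is SAP wording and a small data check. Appendix A already schedules an end-of-treatment marrow examination to confirm CR in patients positive at screening, so no new procedure is needed. The downside is that the CR rate may be slightly lower if the stricter rule is chosen. Because the trial is open-label and the last patient's end-of-treatment visit has taken place (SAP 2.1), the choice should be documented before any results are tabulated.
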